- f Immunology assessments include: total binding and inhibitory antibodies to FIX, and antibodies to CHO protein and rFurin. If an inhibitory antibody with a Nijmegen titer  $\geq 0.6$  BU or total binding antibodies with a positive titer of 1:80 is detected, the test will be confirmed in the central laboratory within 2 weeks of study site notification. In either case the following additional tests will be performed: IgA, IgM, IgG subtypes, and hs-CRP; additional markers may be tested if applicable. If an inhibitor is suspected there may be additional testing for lupus anticoagulans/phospholipid antibodies, or FIX antibody testing with a different methodology. If a subject develops a severe allergic reaction or anaphylaxis the following tests will be performed: hs-CRP, CIC-C1q and CIC-C3 for circulating immune complexes, and IgE. Furthermore, Ig subtypes, inhibitory and total binding antibodies.
- g Immunology testing to be performed at least 3 days (72 h) after the previous infusion of BAX326 and before IP is administered at this visit.
- h CD4 count will be assessed at screening and then every 12 months to confirm the subject's eligibility.
- i At the confirmatory visit in 4 weeks  $\pm 1$  week from screening, the eligibility should be confirmed using the lab results.
- j For subjects switching back to this continuation study from the surgery studyxxvii, the respective visit window may be extended from  $\pm 1$  week to  $\pm 2$  weeks. Every 3 month visits are calculated from Screening for transitioning subjects.
- k Applicable only for subjects receiving a PK-tailored treatment regimen.
- l For a detailed schedule, see Section 21.5.
- m Only in subjects  $\geq 12$  years of age. For details see Section 11.2 TGA testing
- n Pregnancy test as appropriate, and to be repeated during the course of the study in countries where mandated by national law.
- o Prothrombotic markers: TAT complexes, D-dimers, Prothrombin fragment 1.2. Prothrombin markers should also be determined whenever clinically indicated.
- p Only applicable to subjects receiving PK-tailored treatment: After 4  $\pm 1$  weeks of start of treatment with a PK tailored treatment regimen. These subjects have two Week 4 $\pm 1$  visits: first visit = regular visit to confirm eligibility; second visit = visit for PK-tailored subset after 4 weeks of start of PK-tailored treatment regimen and 2 months prior to next scheduled 3-month visit.

---

xxvii Surgery Study 251002 was completed in May 2014. Thirty unique subjects underwent 38 surgeries.

## 21.4 Clinical Laboratory Assessments for Newly Recruited Subjects

**Table 21.4-1**  
**Clinical Laboratory Assessments for Newly Recruited Subjectsa**

Assessments	Screening Visit	First Infusion (ED1)	Study Visit 4 ± 1 Week	StudyVisits: Every 3 Months ± 1 Week j	Study Completion/ Termination Visit d
CD4 count	X			X i	
HIV test and viral load, if positive	X				X
Genetics and HLA-genotype	X o				
Pregnancy Test (if applicable) m	X			X	X
FIX activity	X				
FIX antigen	X				
FIX recovery b		X	X k	X	X
Abbreviated PK k		(X)	(X)	(X)	
Hematology c	X		X	X	X
Clinical Chemistry d	X		X	X	X
Urinalysis e	X		X	X	X
Immunology f	X	X g	X h	X h	X h
Hepatitis serology	X				
INR	X				
TGA l		X	X	X	X
Prothrombotic markers n	X				

*Continued on Next Page*

*Continued*

- a At all assessments, subjects must not be actively bleeding. In addition to the assessments shown, clinical laboratory assessments should be performed whenever clinically indicated.
- b For assessment of recovery: samples will be taken within 0.5 h before the start of the infusion, and at 0.5 h  $\pm$  5 minutes after the infusion. The washout period of at least 5 days (120 h), preferably 7 days, is necessary.
- c Hematology assessments include: hemoglobin, hematocrit, red blood cell count, and white blood cell count with differential (ie, basophils, eosinophils, lymphocytes, monocytes, neutrophils), mean corpuscular volume (MCV), mean corpuscular hemoglobin concentration (MCHC), and platelet count.
- d Clinical chemistry assessments include: sodium, potassium, chloride, bicarbonate, total protein, albumin, alanine aminotransferase (ALT), aspartate aminotransferase (AST), total bilirubin, alkaline phosphatase, blood urea nitrogen (BUN), creatinine, and glucose.
- e Urinalysis assessment: protein. Urinalysis should also be performed if inhibitors are detected.
- f Immunology assessments include: total binding and inhibitory antibodies to FIX, and antibodies to CHO protein and rFurin. If an inhibitory antibody with a Nijmegen titer  $\geq$  0.6 BU or total binding antibodies with a positive titer of 1:80 is detected, the test will be confirmed in the central laboratory within 2 weeks of study site notification. In either case the following additional tests will be performed: IgA, IgM, IgG subtypes, and hs-CRP; additional markers may be tested if applicable. If an inhibitor is suspected there may be additional testing for lupus anticoagulans/phospholipid antibodies, or FIX antibody testing with a different methodology. If a subject develops a severe allergic reaction or anaphylaxis the following tests will be performed: hs-CRP, CIC-C1q and CIC-C3 for circulating immune complexes, and IgE. Furthermore, Ig subtypes, inhibitory and total binding antibodies.
- g Immunology testing to be performed prior to the first infusion of BAX326 at ED1 or PK, if performed at ED1.
- h Immunology testing to be performed at least 3 days (72 h) after the previous infusion of BAX326 and before IP is administered at this visit.
- i CD4 count will be assessed at screening and then every 12 months to confirm the subject's eligibility.
- j For subjects switching back to this continuation study from the surgery studyxxviii, the respective visit window may be extended from  $\pm$  1 week to  $\pm$  2 weeks. Every 3 month visits are calculated from the ED1 visit for newly recruited subjects.
- k Abbreviated PK for FIX and TGA parameters (if subjects  $\geq$  years of age) only in those subjects who are planned to receive a PK tailored treatment regimen. The PK can be performed at any study visit once eligibility is confirmed. A detailed schedule can be found under Section 21.5.
- l To be performed only in subjects  $\geq$  12 years of age. For details see Section 11.2 TGA Testing.
- m Pregnancy test as appropriate, and to be repeated during the course of the study in countries where mandated by national law.
- n Prothrombotic markers: TAT complexes, D-dimers, Prothrombin fragment 1.2. Prothrombin markers should also be determined whenever clinically indicated.
- o If results of FIX gene mutation analysis and HLA genotype are already available at the study site, they will be provided to the sponsor and an additional analysis will not be required.

---

xxviii Surgery Study 251002 was completed in May 2014. Thirty unique subjects underwent 38 surgeries.

**21.5 Abbreviated PK Study for Subjects Receiving PK-Tailored Prophylaxis  
(if newly recruited subjects or PK evaluation not done in BAX 326 Pivotal or BAX326 Surgery)**

**Table 21.5-1  
Abbreviated PK Studyb**

Procedure/ Assessment	Within 0.5 hours Pre-Infusion	BAX326 Infusion	30 ± 5 Min Post-infusion	9 ± 3 hours Post-infusion	24 ± 6 hours Post-infusion	48 ± 6 hours Post-infusion	72 (- 6) hours Post-infusion
FIX activity	X		X	X	X	X	X
TGA parameters a	X		X	X	X	X	X
Infusion of BAX326, at dose of 75 ±5 IU/kg		X					

a TGA parameters: lag time, time to peak thrombin generation, peak thrombin generation, and ETP, only to be performed in subjects ≥ 12 years of age

b Assessment must be performed at least 5 days (120 hours), preferably 7 days, following the previous dose of a FIX product and the subject must not actively bleed and eligibility must be confirmed.

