### **8.1.2 Newly Recruited Subjects**

At least 25 subjects who have not previously been exposed to BAX326 will be enrolled (Cohort 2). Once eligibility criteria are confirmed, subjects will receive prophylactic treatment over a period of up to approximately 100 EDs to BAX326, or until BAX326 is approved in the subject's country, whichever occurs last, but no later than December 31, 2016. A limited number of patients may not have reached 100 EDs by that date and they will continue until they have reached approximately 100 EDs.

---

xiii 1 month calculated on a 30-day basis

The treatment regimen with BAX326 will be at the discretion of the investigator and will consist of one of the following treatment options:

- Standard prophylaxis with twice weekly prophylactic infusions of 50 IU/kg (range of 40-60 IU/kg, which may be increased to 75 IU/kg, in subjects  $\geq$  12 years of age; range of 40-80 IU/kg in pediatric subjects  $<$  12 years), or
- modified prophylaxis determined by the investigator. The dose can be increased up to 100 IU/kg, if applicable; or
- PK-tailored prophylaxis. The maximum dose is 120 IU/kg.

Hemostatic efficacy, safety, and immunogenicity assessments will be performed at Week  $4 \pm 1$ , Month  $3 \pm 1$  week and thereafter every 3 months  $\pm 1$  week (see Section 8.1.1). IR will be determined at the same time points. An additional inhibitor test will be performed immediately before the first exposure to BAX326, as well as an IR during the first infusion of BAX326. The subject will be monitored for vital signs and the occurrence of AEs. Subjects receiving PK-tailored prophylaxis will follow the schedule as described in Section 8.1.3.

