#### **10.3.2 Newly Recruited Subjects (Cohort 2)**

All screening/baseline evaluations must be completed within 42 days or repeated if more than 42 days have elapsed. Exemptions may be granted for administrative reasons by the sponsor, eg, delay in availability of laboratory results. For the purpose of analysis, only the data from the most recent screening visit will be used. If a subject does not satisfy all screening criteria, the same subject may be re-screened at a later date. A complete or partial re-screen may also become necessary at the discretion of the investigator or sponsor. All screening data will be collected and reported in eCRFs, regardless of screening outcome.

---

xix Surgery Study 251002 was completed in May 2014. Thirty unique subjects underwent 38 surgeries.

xx Pivotal Study 250901 and Pediatric Study 251101 have been completed (Last Subject Out: 03 May 2012 [Pivotal] and 14 May 2013 [Pediatric]).

Subjects should not be actively bleeding at the time of screening and at the scheduled study visits, and a wash-out period of at least 5 days, preferably 7 days, should be observed.

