**Newly recruited subjects:**

- At screening
- At ED1/PK prior to the first infusion
- Week 4 $\pm$ 1 week
- Month 3  $\pm$  1 week
- Thereafter, every 3 months  $\pm$  1 week
- At study termination/completion
- Whenever clinically indicated, eg, lack of response to treatment, or severe allergic reactions such as anaphylaxis

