5.3 Definition of Baseline

The most recent value prior to first infusion of IP will be taken as baseline.

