8.1 Analysis of Primary Safety Outcome Measure

The number of possibly or probably related adverse events that occurred during or after first BAX326 infusion will be summarized. In addition, the number of subjects with possibly or probably related adverse events that occurred during or after first BAX326 infusion will be also summarized.

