8.2 Analysis of Secondary Safety Outcome Measures

A table will present the number (%) of subjects for the following safety endpoints: occurrence of inhibitory and (treatment emergent) total binding antibodies to FIX, occurrence of (treatment emergent) antibodies to CHO proteins and rFurin, occurrence of severe allergic reactions (e.g. anaphylaxis), and occurrence of thrombotic events.

As mentioned in section 12.7.1 of the protocol, indeterminate results of total binding antibodies to FIX, antibodies to CHO proteins or rFurin will be set to negative. Occurrence of treatment emergent total binding antibodies to FIX, antibodies to CHO proteins and rFurin is defined by more than 2-dilution increase as compared to levels at screening visit (e.g. negative to 1:80).

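### SAP 8.2 measures treatment-emergent antibodies in Cohort 2 against screening, not the pre-dose ED1 sample, and sets no post-infusion condition on inhibitors, so an antibody arising between the two visits is counted against BAX326

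*Protocol*

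**What the plan says.** The protocol plans two pre-treatment immunology samples for newly recruited subjects. One is at screening. The other is listed in the schedule of immunology tests (Protocol 12.7.1, Table 12.7-1) as "At ED1/PK prior to the first infusion". Protocol 8.1.2 describes it as an addition: "An additional inhibitor test will be performed immediately before the first exposure to BAX326". The laboratory table for these subjects (Table 21.4-1, footnote g) repeats it: "Immunology testing to be performed prior to the first infusion of BAX326 at ED1 or PK, if performed at ED1". Footnote f of that table gives the panel: inhibitory and total binding antibodies to FIX, and antibodies to CHO protein and rFurin.

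Protocol 10.3.2 sets the screening window: "All screening/baseline evaluations must be completed within 42 days or repeated if more than 42 days have elapsed". The sponsor may grant exemptions.

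SAP 5.3 gives a general baseline rule: "The most recent value prior to first infusion of IP will be taken as baseline".

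SAP 8.2 gives a different rule for antibodies. Treatment emergence of binding, CHO and rFurin antibodies "is defined by more than 2-dilution increase as compared to levels at screening visit (e.g. negative to 1:80"). The table is to show "occurrence of inhibitory and (treatment emergent) total binding antibodies to FIX". The treatment-emergent qualifier applies to the binding antibodies but not to the inhibitors. SAP 8.2 does not mention the ED1 sample.

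**The concern.** In a subject who has never received BAX326, the sample drawn immediately before the first infusion shows what was present at first exposure. SAP 8.2 uses an older one. Between the two visits the subject may still be treated with another FIX product: Protocol Table 21.1-1 requires a wash-out from the previous FIX dose both at screening and at ED1.

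An antibody that arises in that interval, whether from the previous concentrate or from assay variation near the detection limit, cannot be caused by BAX326. Under SAP 8.2 it would still be reported as a BAX326 finding. Few positives are expected, so a single misattributed subject could be the whole signal in its row.

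The antibody rule also differs from the SAP's own adverse event rule. SAP 8.1 counts "possibly or probably related adverse events that occurred during or after first BAX326 infusion", and SAP 8.1.1 lists earlier events separately. The antibody table has no equivalent condition.

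**Working it through.** The plan states no figure that could be reproduced: SAP 2.6 says that the sample size has no statistical basis, and no antibody rate is assumed. The check is to apply both written rules to the possible patterns, and then to size one misclassified subject.

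**Step 1. Binding, CHO and rFurin antibodies.** The SAP's own example treats negative to 1:80 as a rise of more than two dilutions, and that is used here.

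| Screening | ED1 pre-dose | Later | SAP 8.2 (against screening) | Against ED1 (SAP 5.3 baseline) |
|---|---|---|---|---|
| negative | 1:80 | 1:80 | emergent | not emergent |
| 1:80 | 1:80 | 1:80 | not emergent | not emergent |
| negative | negative | 1:80 | emergent | emergent |
| 1:80 | negative | 1:80 | not emergent | emergent |

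The rules differ in the first and last rows. In the first row the ED1 value itself already meets the written definition, before any BAX326 was given. SAP 5.2 leaves unscheduled and repeat measurements out of the descriptive statistics, but ED1 is a scheduled visit, so that rule does not remove it.

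**Step 2. Inhibitors.** A titer of at least 0.6 BU at screening is an exclusion criterion (SAP 2.5.2), so it reaches the table only if the subject is enrolled in error. An inhibitor first seen at ED1 is different. The sample is drawn at the infusion visit and tested at the central laboratory, and nothing in the documents requires the result before dosing. Once dosed, the subject is in the FAS (SAP 4.1), and the result meets the unqualified occurrence count in SAP 8.2.

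**Step 3. Size of one subject.** Exact (Clopper-Pearson) 95% intervals:

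- Cohort 2, n = 25 (the planned minimum): 0/25 = 0% (0 to 13.7%); 1/25 = 4.0% (0.1 to 20.4%).
- Pooled, n = about 100 + 25 = 125 (Protocol 8.1): 0/125 = 0% (0 to 2.9%); 1/125 = 0.8% (0.02 to 4.4%).
- Pooled, n = 100, if the total is closer to the figure in Protocol 6.3: 1/100 = 1.0% (0.03 to 5.5%).

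**Step 4. Chance that it happens at all.** The documents give no rate of new positives between screening and ED1. With an assumed rate q per subject, P(at least one in 25) = 1 − (1 − q)^25:

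- q = 0.5%: 12%
- q = 1%: 22%
- q = 2%: 40%
- q = 4%: 64%

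These values of q are illustrative only.

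**The case against.** The case on the other side has substance.

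- *Screening is the programme's established reference.* The integrated safety analysis described in Protocol 6.5 used the same definition against the pre-study screening level, and a specific rule normally overrides a general one. This explains where the SAP 8.2 wording comes from. It does not make the reference right for subjects who have a later sample before first exposure.
- *An ED1-only reference has its own error.* In the last row of the table, a subject with a known earlier antibody would be called emergent. Protocol 6.5 reports two transient rFurin positives at 1:80, so fluctuation at that level is real. This stands, and the fix has to deal with it.
- *A new inhibitor in this interval is remote.* Subjects need at least 150 prior FIX exposure days (50 if under 6 years) and no inhibitor history, and Protocol 6.2 puts the highest risk after 10 to 20 exposure days. This also stands. The inhibitor branch is the less likely of the two.
- *The dates would reveal it.* A pre-dose positive could be recognised from its sample date in a listing. The summary table, as defined, would still count it.

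A reader might infer that the SAP makes no provision for the ED1 sample at all, or that any antibody present before BAX326 is charged to it. Neither is supported. SAP 5.3 would select the ED1 value, and an antibody stable since screening is not counted. A reader might also infer that Cohort 2 was added for immunogenicity. Protocol 6.3 gives the purpose as long-term safety and efficacy in about 100 previously treated patients.

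**Conclusion.** The point holds in a limited form. SAP 8.2 conflicts with SAP 5.3 for Cohort 2. Followed as written, it attributes to BAX326 an antibody that appeared, or rose by more than two dilutions, between screening and the first infusion, an interval of up to 42 days or longer with an exemption. The inhibitor count has no condition that excludes a pre-dose result.

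The scope is Cohort 2 only, but SAP 5 pools the cohorts, so a misattributed case would appear in the overall antibody table without its origin being visible. SAP 5 also splits outcomes by age group, where denominators are smaller. The primary outcome is not affected by this reference, because it counts only adverse events during or after the first infusion.

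The frequency is unknown and probably low. The size of one case (4.0% of 25, or about 0.8% of 125) assumes the planned cohort sizes. The 4.0% describes Cohort 2 on its own, which SAP 8.2 does not tabulate separately.

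**What to change.** Amend SAP 8.2 for Cohort 2 as follows:

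1. Count inhibitory, binding, CHO and rFurin antibodies only from samples taken after the first BAX326 infusion.
2. Take the last pre-infusion sample (ED1 or PK visit) as the reference for treatment emergence, in line with SAP 5.3. Use screening if that sample is missing.
3. List separately any subject positive at screening or at ED1, as present before first infusion. A subject who is positive at screening, negative at ED1 and positive later is then not reported as new without comment.

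The cost is a few sentences and a small programming change, since the protocol already schedules the sample. The drawback is that Cohort 2 would use a different reference visit from Cohort 1 in the pooled table. A footnote can state this.

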## SUMMARY OF CHANGES

**BAX 326 (recombinant Factor IX): Evaluation of Safety, Immunogenicity, and Hemostatic Efficacy in Previously Treated Patients with Severe (FIX level < 1%) or Moderately Severe (FIX level 1-2%) Hemophilia B  
– A Continuation Study**

**Short Title: BAX326 Continuation**

**PROTOCOL NUMBER: 251001**

**AMENDMENT 6 VERSION: 2015 OCT 19**

In this section, changes from the previous global version of the Protocol, Amendment 5, dated 2015 Mar 19, will be described and their rationale will be given.

**1. *Throughout the Document***

Minor grammatical and/or administrative changes have been made to improve the readability and/or clarity of the protocol.

For references to BAX326 Surgery Study 251002 appropriate text or footnotes have been added to make it clear that Surgery Study 251002 was completed in May 2014.

**2. *Section 1 Study Personnel***

The information in this section was aligned with the current protocol template (version 2015 Apr 20).

**3. *Section 2 Serious Adverse Event Reporting***

This section was aligned with the current protocol template (version 2015 Apr 20).

**4. Section 3 Synopsis: Planned Study Period**

***Section 3 Synopsis: Planned Duration of Subject Participation***

***Section 6.5 Evaluation of Anticipated Risks and Benefits of the Investigational Product(s) to Human Subjects***

***Section 7.1 Study Purpose***

***Section 8.1 Overall Study Design***

***Section 8.1.1 Newly Recruited Subjects***

***Section 8.2 Duration of Study Period(s) and Subject Participation***

Description of changes: The maximum study duration per subject was increased from 57 to 68 months. The study completion date was changed from Q4 2015 to Q4 2016. The end of study participation is defined by receiving a product license in the respective country and accumulation of 100 EDs. The end date for subject participation was limited to December 31, 2016 : “... *but no later than December 31, 2016.*” However, if a limited number of newly recruited subjects have not have reached 100 EDs by Dec 31, 2016, these may continue until they have reached approximately 100 EDs.

Reason for changes: According to regulatory authority request, at least 25 additional, BAX326 naïve patients will be enrolled and treated, which is the reason for the study prolongation.

**5. Section 3 Synopsis: Health Related Quality of Life, Patient Activity Level and Pharmacoeconomic Parameters**

***Section 8.3.2.4 Health related Quality of Life, Patient Activity Level and Health Resource Use***

***Section 13.2 Assessment of Health-related Quality of Life and Health Resource Use***

Description of changes: Clarification was provided regarding which age-specific HRQoL measures and questionnaires are applicable at what time to which subject age.

Reason for changes: Due to the addition of Cohort 2 (newly recruited, BAX326 naïve subjects), there was a need for clarifying when the Cohort 2 subjects are to be assigned to the age-specific HRQoL measures and questionnaires.

**6. Section 3 Synopsis: Exploratory Outcome Measures**

**Section 8.3.2.5 Exploratory Outcome Measures**

**Section 11.1.5 Additional Determination of Incremental Recovery in Subjects Receiving Modified or PK-Tailored Prophylaxis**

Description of changes: The text defining the number of subjects in whom TGA parameters will be determined as an exploratory outcome measure has been deleted. It was clarified that TGA parameters pre- and post-infusion concurrent with IR determination for FIX activity will be investigated in a subset of subjects receiving twice-weekly standard or modified prophylaxis including PK-tailored prophylaxis with BAX326 as well as at some selected timepoints during prophylactic treatment.

Reason for changes: Since TGA testing is optional and the assignment of the treatment regimen is at the discretion of the investigator, it cannot be anticipated that a specific number of subjects under a certain treatment regimen will participate in the TGA testing. These circumstances are considered acceptable since the purpose of TGA testing is merely exploratory.

